3.1.4 Age 18 years or older

3.1.5 ECOG performance status ≤ 2 (Karnofsky $\geq 60\%$, see Appendix A)

3.1.6 Participant must have normal organ and marrow function as defined below within 21 days prior to study registration:

- leukocytes	$\geq 3,000/\text{mcL}$
- absolute neutrophil count	$\geq 1,000/\text{mcL}$
- platelets	$\geq 100,000/\text{mcL}$
- total bilirubin	$\leq 2.0 \text{ g/dL}$
- AST(SGOT)/ALT(SGPT)	$\leq 2.5 \times$ institutional upper limit of normal within normal institutional limits
- creatinine	

OR

- creatinine clearance	$\geq 60 \text{ mL/min}/1.73 \text{ m}^2$ for participants with creatinine levels above institutional normal
------------------------	--

3.1.7 Ability to understand and the willingness to sign a written informed consent document

3.1.8 Women of childbearing potential (WOCBP) must agree to use appropriate method(s) of contraception. WOCBP should plan to use an adequate method to avoid pregnancy for 5 months (30 days plus the time required for nivolumab to undergo five half-lives) after the last dose of investigational drug

3.1.9 Women of childbearing potential must have a negative serum or urine pregnancy test (minimum sensitivity 25 iu/l or equivalent units of hcg) at screening. Pregnancy test will be repeated on the day of the first dose of study drug (before administration), although results of this test are not required for registration.

“Women of childbearing potential (WOCBP)” is defined as any female who has experienced menarche and who has not undergone surgical sterilization (hysterectomy or bilateral oophorectomy) or who is not postmenopausal. Menopause is defined clinically as 12 months of amenorrhea in a woman over 45 in the absence of other biological or physiological causes. In addition, women under the age of 55 must have a documented serum follicle stimulating hormone (FSH) level greater than 40 mIU/mL

3.1.10 Men who are sexually active with WOCBP must agree to use any contraceptive method with a failure rate of less than 1% per year. Men who are sexually active with WOCBP will be instructed to adhere to contraception for a period of 7 months after the last dose of investigational product. Women who are not of childbearing potential (ie, who are postmenopausal or surgically sterile as well as azoospermic men) do not require contraception

See Appendix B for further guidance on contraception.

Exclusion Criteria

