3.1.11 Known carcinoma in situ (CIS) or invasive squamous cell carcinoma of the oral cavity. A history of a prior stage III (T1-2N1, T3N0) or IV (T1-3N2, T4N0) invasive head & neck squamous cell carcinoma treated with surgery and radiation with or without chemotherapy. Patients with prior locoregionally advanced tumors treated with surgery alone are eligible.

3.1.12 Existing significant autoimmune conditions. Patients with a history of Hashimoto thyroiditis who are stable on replacement hormone therapy are not excluded. Patients cannot be on long-term (> 4 weeks) corticosteroids at doses exceeding prednisone 20 mg (or its equivalent) prior to enrollment. Short-term corticosteroid dosing is permitted as long as steroids are discontinued within 2 weeks of study registration.

3.1.13 Subject who has had chemotherapy or radiotherapy within 4 weeks (6 weeks for nitrosoureas or mitomycin C) prior to entering the study or those who have not recovered from adverse events due to agents administered more than 4 weeks earlier.

3.1.14 Subject who has been treated with immunotherapy. This includes prior treatment with anti-PD-1, anti-PD-L1, anti-PD-L2, anti-CTLA-4 antibody, or any other antibody or drug specifically targeting T-cell co-stimulation or checkpoint pathways.

3.1.15 Uncontrolled intercurrent illness including, but not limited to, ongoing or active infection, symptomatic congestive heart failure, unstable angina pectoris, cardiac arrhythmia, or psychiatric illness/social situations that would limit compliance with study requirements.

3.1.16 Known human immunodeficiency virus carrier or a diagnosis of immunodeficiency.

3.1.17 Any positive test result for hepatitis B virus or hepatitis C virus indicating presence of virus, e.g., Hepatitis B surface antigen (HBsAg, Australia antigen) positive, or Hepatitis C antibody (anti-HCV) positive (except if HCV-RNA is negative).

3.2.7 A personal history of hematopoietic stem cell or solid organ transplant.

3.2.8 Known non-infectious pneumonitis or any history of interstitial lung disease.

3.2.9 A personal history of other active malignancies, with the exception of non-melanomatous skin cancers, low-risk prostate adenocarcinoma on active surveillance, or treated cancers in remission for the last 5 years.

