4. REGISTRATION PROCEDURES

4.1 General Guidelines for DF/HCC Institutions

An investigator will confirm eligibility criteria and a member of the study team will complete the protocol-specific eligibility checklist.

Eligible subjects will be registered by a member of the study team in the Clinical Trials Management System (CTMS) “OnCore”. Registrations must occur prior to the initiation of protocol therapy. Any subject not registered to the protocol before protocol therapy begins will be considered ineligible and registration will be denied.

Following registration, participants may begin protocol therapy. Issues that would cause treatment delays should be discussed with the Overall Principal Investigator (PI). If a participant does not receive protocol therapy following registration, the participant’s registration on the study must be canceled. Registration cancellations must be made in OnCore as soon as possible.

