6. DOSING DELAYS/DOSE MODIFICATIONS

There will be no dose reductions for nivolumab permitted. Doses of nivolumab may be interrupted, delayed, or discontinued depending on how well the participant tolerates the treatment. Dosing visits are not skipped, only delayed.

Although this is not a phase I protocol, the use of these drugs and the combination in the oral precancerous setting is relatively novel, and therefore we plan to include a safety run-in to ensure that treatment is well tolerated in this setting. A separate safety run in will be performed for the initial study participants, as described in detail in *Section 13, Statistical Considerations*.

Administration of the study drug should be delayed for the following adverse events:

- Grade 2 non-skin, drug-related adverse event, with the exception of fatigue
- Grade 2 drug-related creatinine, AST, ALT and/or Total Bilirubin abnormalities
- Grade 3 skin, drug-related adverse event
- Grade 3 drug-related laboratory abnormality, with the following exceptions:
 - Grade 3 lymphopenia or asymptomatic amylase or lipase does not require dose delay
 - Grade ≥ 3 AST, ALT, Total Bilirubin will require dose discontinuation
- Any adverse event, laboratory abnormality, or intercurrent illness which, in the judgment of the investigator, warrants delaying the dose of study medication.

Note: see Appendix D for guidelines on managing immune-related toxicities

Participants who require delay of nivolumab should be re-evaluated weekly or more frequently if clinically indicated and resume nivolumab dosing when re-treatment criteria (as described below) are met. Participants with a delay in dosing beyond 10 weeks should be considered for discontinuation of protocol treatment and discussed with the Overall PI.

Subsequent dosing may be re-started if subjects continue to meet laboratory criteria (baseline values). The investigator will determine if subsequent dosing is appropriate for subjects who have laboratory or clinical abnormalities that do not meet dose discontinuation criteria (described below). All related grade 2 toxicities should be discussed with the Overall PI, prior to subsequent dosing.

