10. STUDY CALENDAR

Screening evaluations are to be conducted within 3 weeks prior to study registration. Procedures done within a week of study registration don't need to be repeated to establish baseline. Scans and x-rays must be done \leq 4 weeks prior to study registration. In an event that the participant's condition is deteriorating, laboratory evaluations should be repeated within 48 hours prior to initiation of the next cycle of therapy. Each treatment cycle in this study is 28 days long.

Assessments must be performed prior to administration of any study agent. Study assessments and agents should be administered within \pm 3 days of the protocol-specified date, unless otherwise noted.

Studies	Screening	Enrollment	Treatment phase				End of Treatment ^h	Follow up visit 30 days after the last dose ^h	Survival Follow up
			Cycle 1	Cycle 2	Cycle 3	Cycle 4			
			Day	Day	Day	Day			
Informed consent	X								
Medical History	X								
Physical exam (Ht, Wt, VS, PS)	X		X	X	X	X	X	X	
Routine labs ^b	X		X	X	X	X	X	X	
B-HCG (WOCBP only) ^c	X		X	X	X	X	X	X	
FSH test ^d	X								
ECG	X						X		

Photographs, measurements ^e	X		X	X	X	X		X ^h	X ^h
Biopsy samples ^f	X							X	X ^h
Correlative biopsies ^f	X							X	X ^h
Correlative blood			X	X	X	X		X	
Nivolumab			X	X	X	X			
Quality of life survey ^g	X				X		X	X	
Adverse event evaluation			X	X	X	X	X	X	
Survival Status									X ^h

- a) Physical exam is symptom directed. Height measured at screening only.
- b) Routine labs include: CBC with differential, LFTs, chemistries, TSH, phosphorous. Baseline HCV antibody, hepatitis B surface antigen, hepatitis B surface antibody, and hepatitis B core antibody testing is required at screening only.
- c) Serum or urine within 24 hours prior to first dose.
- d) Follicle Stimulating Hormone test will be performed only on women who are under 55 years of age.
- e) Color digital photographs capturing all oral precancerous sites but including the entire oral cavity (any site biopsied should be photographed). Bidimensional measurements of each oral precancerous lesion should be obtained and recorded, using the largest maximum diameter of each site.

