Patients on IV steroids may be switched to an equivalent dose of oral corticosteroids (e.g. prednisone) at start of tapering or earlier, once sustained clinical improvement is observed. Lower bioavailability of oral corticosteroids should be taken into account when switching to the equivalent dose of oral corticosteroids.

Pulmonary Adverse Event Management Algorithm

[figure not shown]
Rule out non-inflammatory causes. If non-inflammatory cause, treat accordingly and continue I-O therapy. Evaluate with imaging and pulmonary consultation.

Patients on IV steroids may be switched to an equivalent dose of oral corticosteroids (e.g. prednisone) at start of tapering or earlier, once sustained clinical improvement is observed. Lower bioavailability of oral corticosteroids should be taken into account when switching to the equivalent dose of oral corticosteroids.

Hepatic Adverse Event Management Algorithm

Rule out non-inflammatory causes. If non-inflammatory cause, treat accordingly and continue I-O therapy. Consider imaging for obstruction.

[figure not shown]
Patients on IV steroids may be switched to an equivalent dose of oral corticosteroids (e.g. prednisone) at start of tapering or earlier, once sustained clinical improvement is observed. Lower bioavailability of oral corticosteroids should be taken into account when switching to the equivalent dose of oral corticosteroids.

*I-O therapy may be delayed rather than discontinued if AST/ALT \leq 8 x ULN and T.bili \leq 5 x ULN.

**The recommended starting dose for grade 4 hepatitis is 2 mg/kg/day methylprednisolone IV.

Endocrinopathy Management Algorithm

[figure not shown]
Rule out non-inflammatory causes. If non-inflammatory cause, treat accordingly and continue I-O therapy. Consider visual field testing, endocrinology consultation, and imaging.

Patients on IV steroids may be switched to an equivalent dose of oral corticosteroids (e.g. prednisone) at start of tapering or earlier, once sustained clinical improvement is observed. Lower bioavailability of oral corticosteroids should be taken into account when switching to the equivalent dose of oral corticosteroids.

Skin Adverse Event Management Algorithm

Rule out non-inflammatory causes. If non-inflammatory cause, treat accordingly and continue I-O therapy.

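### The total bilirubin entry limit in Section 3.1.6 is printed in g/dL, a thousandfold above the mg/dL value evidently meant, so read literally the criterion excludes nobody

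*Combined protocol and SAP*

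**What the plan says.** Section 3.1.6 lists the laboratory values that a participant must have in the 21 days before registration, as the protocol's definition of normal organ and marrow function. The bilirubin row reads "total bilirubin $\leq 2.0 \text{ g/dL". The row for AST and ALT sets 2.5 times the institutional upper limit of normal (ULN).

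Bilirubin appears in two other places, and both concern patients already on treatment:

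- Section 6 works by toxicity grade. Dosing is delayed for "Grade 2 drug-related creatinine, AST, ALT and/or Total Bilirubin abnormalities", and at grade 3 or above "AST, ALT, Total Bilirubin will require dose discontinuation".
- The hepatic algorithm in Appendix C works by multiples of ULN: "I-O therapy may be delayed rather than discontinued if AST/ALT \leq 8 x ULN and T.bili \leq 5 x ULN".

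Section 4.1 makes eligibility a formal step: "An investigator will confirm eligibility criteria and a member of the study team will complete the protocol-specific eligibility checklist". Section 13 builds the primary efficacy population from eligible patients who start treatment. The amendment summaries do not mention the bilirubin unit, so the printed limit is current text.

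**The concern.** Bilirubin limits of this kind are set in mg/dL. With g/dL, the number 2.0 describes a concentration that no patient would reach, so the row stops working as a screen.

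Two things are at stake. The first is safety at entry. Nivolumab's hepatic toxicity has its own management algorithm in this protocol, so bilirubin at baseline matters, and this row is the only bilirubin limit for entry. Section 5.2.1 adds that day 1 laboratory results need not meet the eligibility criteria again, so the screening value is the one that counts.

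The second is the audit trail. Eligibility is confirmed against the written criteria and decides who is counted in the primary analysis. A site that excludes a patient at 4 mg/dL is applying a limit that the protocol does not state. A site that enrols that patient has complied with the protocol as printed.

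**Working it through.** The protocol derives no figure here, so the check is a unit conversion and a comparison with the protocol's other bilirubin rules.

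**Inputs**

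- Printed entry limit: 2.0 g/dL (Section 3.1.6).
- On-treatment threshold up to which delay may replace discontinuation: 5 × ULN (Appendix C, hepatic algorithm).
- Laboratory ULN for total bilirubin: not given in the documents. Assumed range: 1.0 to 1.5 mg/dL.

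**Step 1. Conversion.** 2.0 g/dL × 1,000 mg/g = 2,000 mg/dL. Against 2.0 mg/dL the ratio is 2,000 / 2.0 = 1,000.

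**Step 2. Comparison without assuming a ULN.** For an entry limit of 2,000 mg/dL to lie at or below 5 × ULN, the ULN would have to be at least 2,000 / 5 = 400 mg/dL.

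**Step 3. Comparison over the assumed ULN range.**

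| Assumed ULN (mg/dL) | 5 × ULN (mg/dL) | Printed limit ÷ (5 × ULN) | 2.0 mg/dL ÷ (5 × ULN) | 2.0 mg/dL as a multiple of ULN |
|---|---|---|---|---|
| 1.0 | 5.0 | 2,000 / 5.0 = 400 | 2.0 / 5.0 = 0.40 | 2.0 |
| 1.2 | 6.0 | 2,000 / 6.0 = 333 | 2.0 / 6.0 = 0.33 | 1.7 |
| 1.5 | 7.5 | 2,000 / 7.5 = 267 | 2.0 / 7.5 = 0.27 | 1.3 |

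Read as printed, the entry limit is about 267 to 400 times looser than the on-treatment threshold. Read as mg/dL, it is 1.3 to 2.0 times ULN and lies below that threshold, as an entry limit should.

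**Step 4. Wording.** The list is there to define normal organ function. A limit of 2,000 mg/dL cannot serve that purpose, and 2.0 mg/dL can. This argument needs no ULN.

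**Step 5. Reach.** The design figures in Section 13 do not use bilirubin. Recomputed by exact binomial, they match the protocol: early stopping 51.5% and a positive conclusion 9.8% at a 10% response rate, a positive conclusion 84.3% at 25%, and suspension for toxicity 7%, 32% and 62% at rates of 10%, 20% and 30%.

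**The case against.** The strongest objection is that the point rests on one missing letter in a table that was visibly damaged when the PDF was read. The creatinine limit has moved onto the AST/ALT row and left its own cell empty. A dropped m cannot be ruled out from this text alone. That stands, and it is why the source PDF must be checked first. It does not dispose of the point: the visible damage is a displaced cell, whereas the bilirubin row keeps its label, number and a complete unit, and the other units in the table look intact.

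A second objection is that the 5 × ULN comparison relies on an assumed ULN. It also comes from a footnote to a generic algorithm whose figure is not shown, while Section 6 sets its own rule by grade. This is fair. The multiples are only supporting evidence; the case rests on the factor of 1,000 and on the stated purpose of the list.

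A third objection is that nothing would go wrong in practice. The transaminase limit remains. So do the exclusions for "Uncontrolled intercurrent illness including, but not limited to, ongoing or active infection" and for "Any positive test result for hepatitis B virus or hepatitis C virus indicating presence of virus". Liver tests are done at screening and in every cycle (Section 10, footnote b: "Routine labs include: CBC with differential, LFTs, chemistries, TSH, phosphorous"). The delay and discontinuation rules also apply, and the eligibility checklist, which is not in the documents, may already carry the right unit. This largely stands and keeps the point minor. It does not make the printed criterion correct.

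**Conclusion.** The point holds and is minor. Section 3.1.6 as printed sets the bilirubin entry limit at 2,000 mg/dL, 1,000 times the 2.0 mg/dL evidently intended, and nothing else in the protocol supplies or corrects it. That the literal limit excludes nobody rests on the clinical assumption that no patient approaches 2,000 mg/dL; the documents do not say so. The multiples of the on-treatment threshold rest on an assumed ULN of 1.0 to 1.5 mg/dL. Confidence is medium, because the unit has not been seen in the source PDF. No endpoint, sample size, error rate or analysis is affected.

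**What to change.** Check the unit in the source PDF. If it reads g/dL, amend the bilirubin row of Section 3.1.6 to 2.0 mg/dL or less, and confirm that the protocol-specific eligibility checklist carries the same unit. The cost is a one-word correction and a check of one form, with no change to design, sample size or analysis. If the source already reads mg/dL, the protocol needs no change.

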3.2 Inclusion of Women and Minorities

Both men and women of all races and ethnic groups are eligible for this study.

4. REGISTRATION PROCEDURES

4.1 General Guidelines for DF/HCC Institutions

An investigator will confirm eligibility criteria and a member of the study team will complete the protocol-specific eligibility checklist.

Eligible subjects will be registered by a member of the study team in the Clinical Trials Management System (CTMS) “OnCore”. Registrations must occur prior to the initiation of protocol therapy. Any subject not registered to the protocol before protocol therapy begins will be considered ineligible and registration will be denied.

Following registration, participants may begin protocol therapy. Issues that would cause treatment delays should be discussed with the Overall Principal Investigator (PI). If a participant does not receive protocol therapy following registration, the participant’s registration on the study must be canceled. Registration cancellations must be made in OnCore as soon as possible.

4.2 Registration Process for DF/HCC Institutions

DF/HCC Standard Operating Procedure for Human Subject Research Titled *Subject Protocol Registration* (SOP #: REGIST-101) must be followed.

5. TREATMENT PLAN

Treatment will be administered on an outpatient basis. No investigational or commercial agents or therapies other than nivolumab (BMS-936558) may be administered with the intent to treat the participant’s oral high-risk leukoplakia during the course of treatment.

5.1 Pre-Treatment Criteria

Eligibility and exclusion criteria are provided in Section 3. These criteria will be assessed 21 days prior to study registration to establish eligibility and baseline values.

Informed consent will be obtained after the study has been fully explained to the subject and before the conduct of any screening procedures or assessments.

Demographic information and baseline characteristics will be collected at the Screening Visit. Standard demographic parameters include age, sex, and race/ethnicity (recorded in accordance with prevailing regulations). Baseline characteristics will include ECOG PS (Appendix A), disease status, and focused medical histories.

5.2 Treatment Regimen

Pre-medications are not required. There is no need to wait for the result of TSH level to treat. Each treatment cycle will be 28 days long. Nivolumab infusion must be promptly followed by a saline flush to clear the line of nivolumab. Participants should be carefully monitored for

infusion reactions during nivolumab administration. If an acute infusion reaction is noted, participants should be managed according to the algorithm described in Appendix D.

Nivolumab 480 mg will be administered by IV infusion on Day 1 of each 28-day cycle. Treatment with the study drug will continue for a maximum of 4 cycles or until unacceptable toxicity or withdrawal of consent. Nivolumab will be administered over 60 +/-10 minutes via a low protein binding infusion set with 0.2-1.2 micron in-line filter.

5.2.1 Cycle 1, Day 1

If screening assessments occur within a week before start of study treatment, then they may serve as the baseline cycle 1 day 1 visit and cycle 1 day 1 labs do not need to be performed. Day 1 labs do not need to re-meet eligibility criteria.

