The specimen must arrive in a timely fashion to facilitate processing for evaluation of immune cells. Blood must be spun within 3 hours of collection for 15 min at 3000 rpm. The plasma is then aliquoted into 2 x 60 μ L aliquots and immediately frozen at -80°C. Plasma is thawed on ice prior to usage. 50 μ L of plasma is sufficient for each assay, where triplicate measurements per sample per time point are envisaged. Plasma is diluted 1:4 (15 μ L in 50 μ L reaction) prior to transfer to plate-based assay. We will utilize a multiplex magnetic bead-based sandwich ELISA assay to simultaneously measure the soluble form of 14 immune checkpoint molecules (BTLA, CTLA-4, PD-1, PD-L1, PD-L2, GITR, HVEM, IDO, LAG-3, TIM-3, CD27, CD28, CD80 and CD137). Each bead is encoded with a ratiometric concentration of 2 IR dyes and act as a barcode, unique to each protein. The final detection complex is formed with the addition of streptavidin-phycoerythrin (SA-PE) conjugate, where the phycoerythrin serves as the fluorescent reporter. Plasma concentration levels, measured in pg/mL, for each protein are derived from 5-parameter curve fitting models. Fold change relative to pre-treated baseline are calculated and plotted as log2FC to establish biological significance. The changes in secretion levels will be correlated with tumor immune parameters and clinical response.

Immunohistochemistry

At the time of pre- and post-treatment biopsy, one core of fresh tissue will be allocated to a standard orange-top specimen cup containing 10% neutral buffered formalin. The specimen will be labeled with the participant's initials, medical record number and the date of acquisition. After collection, the specimen will be sent to the Brigham & Women's Hospital (BWH) pathology division for processing. Following standard tissue processing, sectioning and slide preparation for histopathologic review, the specimen will be stored in accordance with BWH protocols (both tissue blocks and tissue slides). At a later time, we will then request tissue block retrieval through the Pathology Specimen Locator Core with preparation of 5 unstained slides through the Specialized Histopathology (SHP) Core service at BWH. SHP will then prepare 1 stained

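### The Section 5.2.1 waiver of Cycle 1 Day 1 has no exceptions, so it conflicts with the first-dose pregnancy test rules and leaves the pre-dose correlative blood draw unprotected

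*Combined protocol and SAP*

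**What the plan says.** Section 5.2.1 sets a condition, "If screening assessments occur within a week before start of study treatment", and then gives the consequence: "they may serve as the baseline cycle 1 day 1 visit and cycle 1 day 1 labs do not need to be performed". It lists no items that fall outside the waiver. It adds only that Day 1 labs need not satisfy the eligibility limits again.

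On the pregnancy test, Section 3.1.9 asks for a negative result at screening and then a second test: "Pregnancy test will be repeated on the day of the first dose of study drug (before administration". It notes that this second result is not needed for registration. The Section 10 calendar gives B-HCG its own row, marked at both Screening and Cycle 1, and footnote c reads "Serum or urine within 24 hours prior to first dose".

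Section 10 also has a one-week allowance of its own. Procedures done within a week of registration need not be repeated to establish baseline.

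On research blood, the calendar row "Correlative blood" is blank at Screening and Enrollment and marked at Cycles 1 to 4 and at the 30-day visit. The calendar preamble says "Assessments must be performed prior to administration of any study agent". Footnote b defines a separate row: "Routine labs include: CBC with differential, LFTs, chemistries, TSH, phosphorous". Section 9.1 ties two tubes of blood to the pre-treatment and post-treatment biopsies as well as to other time points, but refers to the calendar for collection times. It uses the pre-dose value as the reference: "Fold change relative to pre-treated baseline are calculated".

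**The concern.** A waiver that replaces a whole visit should say which parts of the visit it replaces. This one does not, and two Cycle 1 items depend on being done close to the first dose.

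The first is the pregnancy test. A site that follows 5.2.1 to the letter could give the first dose on a screening result several days old and believe it had complied, while breaching 3.1.9 and footnote c. This bears on participant safety.

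The second is the correlative blood. Its Cycle 1 sample is the calendar's only one before first dose, and pre-dose plasma cannot be collected later. A participant without it has no reference value for the fold change in Section 9.1 and cannot enter the paired comparison of circulating markers in Section 13.

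**Working it through.** **Pregnancy test.** The table applies each rule to the age of the test at first dose, taking 5.2.1 literally and assuming that the test was part of screening.

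| Age of test at first dose | 3.1.9 | Footnote c | 5.2.1 |
|---|---|---|---|
| Same day, before the infusion | meets | meets | meets |
| Previous day, within 24 hours | fails | meets | meets |
| More than 24 hours, up to 7 days | fails | fails | meets |
| More than 7 days | fails | fails | fails |

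The third row is the conflict: one rule is met and two are not. The second row is a smaller mismatch between 3.1.9 and footnote c. Those two are nested, because a same-day pre-dose test satisfies both.

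**The two one-week clocks.** Section 5.2.1 counts back from start of treatment and Section 10 from registration. Whenever treatment starts after the day of registration, a procedure can be inside the Section 10 week and outside the 5.2.1 week. For example, a procedure 6 days before registration with treatment 3 days after it is 6 + 3 = 9 days old at first dose.

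**Correlative blood.** Before first dose the calendar schedules one draw, at Cycle 1. It is pre-dose because assessments precede study agent. No screening sample exists on the calendar to take its place. Section 9.1 implies a draw at the pre-treatment biopsy, which the calendar footnotes allow at any time from consent up to Cycle 1 Day 1, but the calendar does not mark blood there.

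**Does the planned power suffer?** Section 13 states 80% power for 27 pairs, a 0.58 SD mean difference and a two-sided 0.05 Wilcoxon signed-rank test. To reproduce this, I used the paired noncentral t with the Wilcoxon efficiency 3/π (about 0.955):

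- effective n = 27 × 0.955 = 25.8
- noncentrality = 0.58 × √25.8 = 2.95
- power = 0.808

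Simulation of the exact signed-rank test with normal differences (40,000 runs) gives 0.810. The stated 80% is reproduced.

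The number treated, if the trial completes its second stage, is 33. The margin before fewer than 27 pairs remain is 33 − 27 = 6, or 6/33 = 18%. The documents give no rate of waiver use, so any number of lost draws is an assumption:

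- 3 lost: 33 − 3 = 30 pairs (power about 0.85)
- 5 lost: 33 − 5 = 28 pairs, still above 27

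The six spare patients must cover missing samples for every reason, not only for this one.

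**The case against.** The best defence is that 5.2.1 is a convenience rule and that specific provisions prevail over it. Section 3.1.9 describes a second test in addition to screening, and the calendar marks B-HCG at both visits, so a screening result was never meant to replace it. That is probably the intent. It does not remove the conflict, because 5.2.1 is also specific to Cycle 1 Day 1, waives its labs without reservation, and states no order of precedence.

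On the blood draw the defence is stronger, and most of it stands. Screening can serve only for what was done at screening, and the calendar has no correlative blood there. The Section 10 allowance concerns repeats, and a first draw is not a repeat. The row is separate from the routine labs, and the sentence about eligibility limits suggests that clinical labs were meant. The participant still attends for the infusion. A reader might infer that the waiver removes the pre-dose plasma, but the documents do not say so. What remains is that 5.2.1 replaces the baseline visit as well as its labs, and that the biopsy draw in Section 9.1 is not on the calendar.

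A reader might also subtract lost draws from 27 and conclude that power falls below 80%. That holds only if all six spare patients are already lost for other reasons, and nothing in the documents says that they are.

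**Conclusion.** The plan is wrong as written on the first-dose pregnancy test. A result more than 24 hours and up to 7 days old is acceptable under 5.2.1 taken literally and unacceptable under both 3.1.9 and footnote c. The number of women concerned is probably small: Section 2.1 puts mean age at diagnosis of oral proliferative verrucous leukoplakia in the seventh decade. That is an inference, since the documents give neither a count of women of childbearing potential nor an age for the other eligible diagnoses.

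For the correlative blood, the finding is a risk caused by loose wording. It would touch only the circulating-marker comparison, which Section 13 calls exploratory. Tumor marker baselines come from the biopsy, and the primary response analysis does not use the blood. No shortfall against the stated 80% power is shown when 33 patients are treated. If the trial stopped after the first 16, 27 pairs could not be reached whatever the waiver said.

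**What to change.** - Reconcile 5.2.1, 3.1.9, calendar footnote c and the one-week sentence in Section 10. The sponsor should state one rule for the first-dose pregnancy test and use it in all places. Which rule that is remains the sponsor's clinical decision.
- In 5.2.1, list the Cycle 1 Day 1 items that the waiver covers, and state whether the week runs from registration or from start of treatment.
- In 5.2.1, state that the pre-dose correlative blood draw is not waived.
- Make Section 9.1 and the calendar agree on when the baseline blood is taken.

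The cost is a few sentences in an amendment. No procedure is added, because the pregnancy test and the blood draw are both already marked at Cycle 1. The 27 pairs and 80% power in Section 13 need no change on this account.
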